### **2.6.3 Safety measures**

Adverse events (AEs) are recorded at each visit and at follow-up phone call. When applicable, adverse events will be noted specifically in association with the study and non-study eyes.

Best corrected visual acuity (BCVA) and biomicroscopy (Slit-Lamp) and external eye exam are performed at each visit.

A urine pregnancy test will be performed at screening for all female subjects of child-bearing potential.

#### **2.6.4 Other measures**

Concomitant medications associated with the treatment of study and non-study eyes will be specifically noted as such.

### **2.7 Drug Concentration and PK Measurements**

No drug concentration measures will be taken in this study.

### **2.8 Handling of Missing, Incomplete, and Repeat Data**

For efficacy parameters, missing or invalid data for pinch pain assessment will be assessed for each assessment time point post dose. Missing values that occur either within 5 minutes (inclusive) post dose or after 5 minutes post dose, due to either invalid data or early termination, will be imputed with the method of last-observation-carried-forward (LOCF) for the planned assessment time points on Day 1.

For safety parameters, missing or invalid data will be treated as missing for the corresponding assessment of a visit.

All data records are identified by study visit and/or assessment time point. Should repeated data records exist within a study visit and/or assessment time point, the first valid data record will be utilized for any statistical analyses of the corresponding study visit and/or assessment time point. All existing data records including the repeat data records in the study database will be presented in data listings and CRF data tabulations.

Any resultant incomplete or missing data of either efficacy or safety parameters will be treated as missing in the statistical analyses involving these parameters.

### **2.9 Statistical Methods**

Unless specified otherwise, SAS® Version 9.0 or higher will be utilized to perform the statistical analyses of efficacy and safety measures.

Categorical variables will be summarized in general using frequencies and percentages, whereas continuous variables will be summarized in general using descriptive statistics of number of observations (n), mean, standard deviation (SD), minimum (Min), median, and maximum (Max).

In both data listings and CRF domain data tabulations, subject ID will consist of site number plus the subject screening number in the format of XXX-YYY, where XXX denotes the site number and YYY the subject's screening number within the site.

Hypothesis testing, unless otherwise indicated, will be performed at the 5% significance level. All p-values will be rounded to four decimal places; p-values less than 0.0001 will be presented as '<0.0001' in all tables. All group comparisons from analysis of variance (ANOVA) and/or analysis of covariance (ANCOVA) models will be based on Type III sums of squares. In the case of substantial non-normality, results from non-parametric tests will also be reported. All confidence intervals (CI) will be two-sided with 95% coverage.

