9.2 Sample Size Considerations

Efficacy:

With 60 subjects per treatment group and assuming 15% response in the placebo group, this study will have 88% power to detect a treatment effect of at least 25% between AG-920 and placebo ($\alpha=0.05$, two-sided).

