9.4 Statistical methods to be employed

9.4.1 General Considerations

All continuous study assessments will be summarized by treatment and time point (as applicable) using descriptive statistics (n, mean, median, standard deviation, minimum, and maximum). All categorical study assessments will be summarized by treatment and time point (as applicable) using frequency counts and percentages.

Hypothesis testing, unless otherwise indicated, will be performed at a two-sided 0.05 significance level. Where applicable, two-sided 95% confidence intervals will be reported. All p-values will be displayed to four decimal places, with p-values less than 0.0001 presented as '<0.0001' and p-values greater than 0.9999 presented as '>0.9999'. Difference between Articaine Sterile Topical Ophthalmic Solution (AG-920) and Placebo will be calculated as Articaine Sterile Topical Ophthalmic Solution –Placebo.

All study data will be listed by treatment, subject, time point, and eye (as applicable).

Statistical methods will be more fully described in a separate document (Statistical Analysis Plan).

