#### **2.5 Sample Size Estimation**

The study is intended to test for a difference in proportion of subjects with anesthetic response (i.e., no pain) between AG-920 and placebo at 5 minutes post dose.

Assuming a 25% delta in proportion between AG-920 and placebo groups and an anesthetic response (i.e., no pain at 5 minutes post dose) to placebo of 15%, a sample size of 60 per group will provide a statistical power of 88% at the significance level of 0.05 (2-sided), with a Chi-square test without continuity correction.

Therefore, a total of 120 subjects randomized with an equal allocation ratio (1:1) of the active versus placebo will be needed in the present study.

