### 2.9.2 Secondary efficacy analysis

The secondary efficacy endpoints include 1) the onset of anesthetic effect defined as the time to no pain by conjunctival pinch within 5 minutes post application of the dose; and, 2) the duration of anesthetic effect defined as the time from the onset of anesthetic effect to the time point when pinch pain resumes. Secondary efficacy endpoints will be analyzed for the ITT population and PP population.

Prior to the determination of the secondary efficacy variables, handling of missing values that occur prior to or at 5 minutes post dose or after 5 minutes post dose on Day 1 is described in Section 2.8.

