### Duration of anesthetic effects

The secondary endpoint of the duration of anesthetic effect in minutes from the onset of anesthetic effect to the time point when pinch pain resumes is defined in Section 2.6.2. This endpoint will be compared for between-group differences, using a 2-way ANOVA model with treatment (the effect of interest) and study eye side as the effects. The study-eye-side effect is used as a blocking factor in the model to control the potential treatment differences among the sites.

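### Onset and duration are each tested at two-sided 5% with no gate on the primary, no order and no adjustment, so a false nominal secondary finding has a chance of up to about 10%

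*SAP*

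**What the plan says.** **Level.** SAP 2.9: "Hypothesis testing, unless otherwise indicated, will be performed at the 5% significance level". Protocol 9.4.1 adds the sidedness: "Hypothesis testing, unless otherwise indicated, will be performed at a two-sided 0.05 significance level". Neither document indicates anything different for the secondary endpoints.

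**Secondary tests.** SAP 2.9.2 has two secondary efficacy endpoints, onset and duration. Under each it writes: "This endpoint will be compared for between-group differences, using a 2-way ANOVA model with treatment", with study eye side as the other factor. It also states: "Secondary efficacy endpoints will be analyzed for the ITT population and PP population". SAP 4.5.2 plans inferential statistics for both endpoints in both populations (Tables 2.3.1, 2.3.2, 2.4.1 and 2.4.2).

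**Extra tests.** SAP 2.9: "In the case of substantial non-normality, results from non-parametric tests will also be reported". No non-parametric test is named, no threshold is given for the trigger, and nothing says which result prevails.

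**Ranking of populations.** Protocol 9.3 and 9.4.6 and SAP 3.1 and 4.1 make ITT the primary efficacy population. PP is secondary, and Protocol 9.4.6 describes it as a repeat to check robustness.

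**Claim rule.** Protocol 9.4.6 and SAP 2.9.1 say when superiority will be claimed, and only for the primary endpoint. The readable text contains no claim rule for the secondaries and no statement that they are descriptive.

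**The concern.** This is a Phase 3 trial, and onset and duration answer two of its named secondary objectives. Each is tested at the full 5%, whether or not the primary succeeds. A nominally significant onset or duration result could therefore be presented after a failed primary. With two such tests, the 5% level does not hold for the pair.

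The open rule on non-parametric results adds to this, because its trigger may well be met. By SAP 2.6.2 the planned onset times take only four values: 0.33, 0.67, 1.0 and 5 minutes. Duration also rests on a coarse set of pinch times. With no rule fixed in advance, which result to stress could be settled after unmasking.

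**Working it through.** **1. The plan's own figure.** The documents give no error rate for the secondaries. Their one design figure is the power for the primary. Inputs: "With 60 subjects per treatment group and assuming 15% response in the placebo group" (Protocol 9.2) and "Assuming a 25% delta in proportion between AG-920 and placebo groups" (SAP 2.5), so 15% against 40%, 60 per group, two-sided 5%, uncorrected chi-square.

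- Pooled proportion: (0.15 + 0.40)/2 = 0.275.
- SE under no difference: √(2 × 0.275 × 0.725/60) = 0.0815.
- SE under the alternative: √((0.15 × 0.85 + 0.40 × 0.60)/60) = 0.0783.
- Power: Φ((0.25 − 1.96 × 0.0815)/0.0783) = Φ(1.15) = 87.6%. Exact enumeration gives 88.6%.

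The stated 88% is reproduced. It concerns the primary only.

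**2. Two governing tests (ITT ANOVA on onset and on duration), no true difference in either.**

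- Independent: 1 − 0.95² = 9.75%.
- Upper bound under any dependence: 0.05 + 0.05 = 10%.
- Correlated, by bivariate normal: 9.5%, 9.1%, 8.3% and 7.0% at correlations 0.3, 0.5, 0.7 and 0.9. Duration is computed by subtracting onset, so some correlation is plausible.
- False findings in favour of AG-920 only: 1 − 0.975² = 4.9%, at most 0.025 + 0.025 = 5%.

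**3. If either the ANOVA or a non-parametric test could count (ITT only).** This needs assumptions that the documents do not supply. The simulation used 4,000 runs per scenario with:

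- 9 vs 24, 16 vs 17 or 9 vs 48 analysed subjects (9 and 24 are 15% and 40% of 60);
- onset at 20, 40 or 60 seconds or 5 minutes with probabilities 0.4/0.3/0.2/0.1 or 0.25 each;
- pain return at 10, 15, 20, 25 or 30 minutes with probabilities 0.3/0.3/0.2/0.1/0.1;
- an ANOVA with eye side and a Wilcoxon test, the latter always run.

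| Result that may count | Chance of at least one P ≤ 0.05 |
|---|---|
| One endpoint, ANOVA | 3.3% to 5.5% |
| Both endpoints, ANOVA | 7.9% to 10.0% |
| Both endpoints, ANOVA or Wilcoxon | 12.2% to 14.2% |

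The Monte Carlo standard error near 13% is √(0.13 × 0.87/4000) = 0.5 points. The simulation is a simplification. Pinches at 40 and 60 seconds and 5 minutes mean that pain can return before 10 minutes. Subjects who reach onset are also not the same group as 5-minute responders.

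**4. With a hierarchy.** In a fixed sequence (primary, onset, duration, each at 5% and only if the step before is significant), a false finding requires rejecting the first true null in the sequence. Familywise error is therefore at most 5%. The same bound holds for a gate followed by Holm. A gate alone is not enough: if the primary effect is real and the gate opens, two unordered secondaries still carry up to 10%.

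**The case against.** The strongest reply is that the plan already settles more than it might seem.

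- **Population.** A reader might count two endpoints, two populations and two tests as eight equal chances; with an assumed 5% to 10% excluded from PP, simulation of that reading gives about 15% to 18%. The documents do not support it, since ITT is ranked first and PP is a robustness repeat. This part of the objection stands.
- **Test.** ANOVA is the only test named for each endpoint, and the non-parametric results are reported in addition to it. Choosing whichever is favourable is not something the plan provides for. This also stands, but it leaves the gap in SAP 2.9: no trigger, no named test and no rule for disagreement.
- **Claims.** With no secondary claim rule, the 10% is the chance of a nominal finding, not of a false claim. That is correct. But nothing labels these tests descriptive, and inferential results are planned for both.
- **Direction.** Only about 5% of the chance favours AG-920. Correct.
- **Choice of test.** A reader might conclude from the coarse pinch times that a rank test should govern. The protocol's endpoints are a mean time to onset and a mean duration, which a rank test does not compare. ANOVA also showed no inflation of note in the simulation (at most 5.5% per endpoint), so the error rate gives no reason to displace it.

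**Conclusion.** The point holds in a limited form. Two secondary endpoints are each tested at two-sided 5% with no gate, order or adjustment. The chance of at least one false nominal finding is up to about 10%, of which about 5% favours AG-920. This rests on the documents' own alpha and on there being no true difference among the subjects analysed; positive correlation lowers it somewhat.

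The 12% to 14% applies only if an ANOVA or a non-parametric result could equally count. It depends on assumed distributions and should not be read as a property of the plan. Nor should a reader infer that the primary is compromised, because its 5% error is unaffected. What is at stake is the standing of any nominal onset or duration result, above all after a failed primary.

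**What to change.** Add to SAP 2.9.2:

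- The secondary endpoints are tested in ITT only if the primary is significant.
- They are then tested either in a pre-stated fixed sequence, for example onset and then duration, each at two-sided 5%, or by Holm (smaller p-value against 2.5%, the other against 5%).
- The named two-way ANOVA governs each endpoint. Non-parametric and PP results are supportive.

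If no confirmatory use is intended, state instead that the secondary p-values are descriptive.

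This needs wording only, with no new data, and N stays at 120. The price is that no secondary claim can follow a failed primary. Under a fixed sequence the second endpoint cannot be claimed if the first fails; under Holm there is a small loss of power.

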### 2.9.1 Primary efficacy analysis

The primary efficacy endpoint for this study is the proportion of subjects with anesthetic response defined as no pain at 5 minutes post application of the dose. The definition of the primary efficacy endpoint is given in Section 2.6.1. The non-parametric Cochran-Mantel-Haenszel (CMH) test with adjustment for study eye side will be used to examine the difference in proportion of subjects with anesthetic response at 5 minutes post dose between the active treatment group and placebo group. If the proportion of subjects (expressed as a percentage) is higher in the AG-920 group and the  $P$  value is statistically significant ( $P \leq 0.05$ ), then superiority of AG-920 over placebo will be claimed.

Between-group difference and its 95% confidence interval (CI) in the proportion of subjects with anesthetic response (yes=1) vs. non-response (no=0) will be calculated using a two-way analysis of variance (ANOVA) model with treatment (the effect of interest) and study eye side as the effects. The study-eye-side effect is used as a blocking factor in the model to control the potential treatment differences among the study eye sides.

The primary efficacy analysis will be performed for the ITT population, which will include all of the randomized subjects who received the complete application of one study dose (i.e., two drops). The analysis model adjusts for the effect of the study eye side. The study-eye-side by treatment interaction will be examined through the summary descriptive statistics of subjects with anesthetic response for each study eye side.

Prior to the determination of the primary efficacy variable, handling of missing values that occur prior to or at 5 minutes post dose is described in Section 2.8.

The primary efficacy endpoint will also be analyzed for the PP population as well as for subgroups of the ITT population, such as male vs. female, Caucasian vs. Non-Caucasian, age groups, and iris color dark brown vs. other colors.

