9.4.6 Analysis of Efficacy

Analyses will be performed primarily on the ITT population and will be repeated on the PP population to determine robustness of results. For the primary efficacy endpoint of the proportion of subjects with no pain at 5 minutes, a Pearson chi-square test will be used for the comparison of the two proportions from the two treatment groups. In addition, a two-sided 95% confidence interval for the difference in response rates between the two treatment groups will be calculated. If the lower limit of the 95% confidence interval is greater than 0 and the P value is statistically significant ($P < 0.05$), then superiority of AG-920 over the placebo will be claimed.

Sub-group analyses based upon pre-study characteristics such as sex, iris color, age, and race may be completed to further investigate the efficacy and safety measures.

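### The primary confidence interval comes from a pooled-variance ANOVA on yes/no data: sound at the planned rates with equal arms, but able to under-cover with unequal arms or widely separated rates

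*SAP*

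**What the plan says.** SAP 2.9.1 tests the primary endpoint, no pain at 5 minutes, with a Cochran-Mantel-Haenszel (CMH) test adjusted for study eye side. The between-group difference and its 95% interval are separate: they "will be calculated using a two-way analysis of variance (ANOVA) model with treatment (the effect of interest) and study eye side as the effects", with response coded 1 and non-response 0. SAP 2.9.1 and 4.5.1 carry the same analysis to subgroups by sex, age, race and iris colour. No binomial or score-type interval is planned. The remedy in SAP 2.9 for marked non-normality adds non-parametric tests, not another interval.

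The SAP superiority rule uses the CMH P value and the direction of the effect, and has no interval condition. Protocol 9.4.6 does have one: "If the lower limit of the 95% confidence interval is greater than 0", together with a significant Pearson chi-square test. It does not say how that interval is computed.

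The planning figures are in SAP 2.5: "Assuming a 25% delta in proportion between AG-920 and placebo groups", 15% response on placebo and 60 per group, sized "with a Chi-square test without continuity correction".

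**The concern.** An ANOVA assumes one common variance. A binary response has variance p(1 − p), which differs between arms whenever the rates differ. With equal arms the two variances average out and the interval is close to a Wald interval with a t quantile. With unequal arms the pooled variance gives the wrong weight to each arm. Like a Wald interval, it is also symmetric and unbounded, so it behaves poorly when one rate is near 0 and the other near 1.

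At stake is the accuracy of the reported effect size and of the subgroup intervals. When rates are far apart, the misses fall mainly on one side: the lower limit is too high, which overstates the minimum benefit.

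**Working it through.** **Inputs.** From SAP 2.5: placebo 15%, active 15% + 25% = 40%, 60 per arm, two-sided 0.05. From SAP 2.9.1: the ANOVA interval. All other rates and arm sizes below are assumptions.

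**The plan's power.** The mean rate is 0.275. Power = Φ[(0.25√60 − 1.96√(2 × 0.275 × 0.725)) / √(0.15 × 0.85 + 0.40 × 0.60)] = Φ[(1.936 − 1.238)/0.606] = Φ(1.153) = 87.6%. Exact enumeration of the uncorrected chi-square test gives 88.6%. The stated 88% is reproduced.

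**The ANOVA interval.** Taking no eye-side effect, the limits are d ± t(N − 3) × √[MSE × (1/nA + 1/nP)], where MSE = [nA pA(1 − pA) + nP pP(1 − pP)]/(N − 3).

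At 24/60 versus 9/60: MSE = (14.40 + 7.65)/117 = 0.1885; SE = √(0.1885 × 2/60) = 0.0793; t = 1.980. The limits are 25.0% ± 15.7%, or 9.3% to 40.7%. Newcombe gives 9.1% to 39.4% and Miettinen-Nurminen 9.2% to 40.0%.

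**Why balance matters.** Compare the variance that the ANOVA targets with the true variance of the difference at 40% versus 15%, leaving aside the degrees-of-freedom divisor:

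- 55 active, 65 placebo: true 0.24/55 + 0.1275/65 = 0.00633; pooled (13.20 + 8.29)/120 × (1/55 + 1/65) = 0.00601. SE ratio √(0.00601/0.00633) = 0.97.
- 20 active, 40 placebo: true 0.01519; pooled (4.80 + 5.10)/60 × 0.075 = 0.01238. SE ratio 0.90.
- 40 active, 20 placebo: true 0.01238; pooled (9.60 + 2.55)/60 × 0.075 = 0.01519. SE ratio 1.11.

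**Exact coverage.** Every possible table was enumerated (61 × 61 = 3,721 at 60 per arm) and weighted by its binomial probability. Miettinen-Nurminen (M-N) coverage is the probability that its score statistic at the true difference lies within ±1.96. A two-sided 95% interval should have its lower limit above the truth 2.5% of the time.

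| Rates, active/placebo | n, active/placebo | ANOVA coverage | ANOVA lower limit above truth | ANOVA upper limit above 100% | Newcombe coverage | M-N coverage |
|---|---|---|---|---|---|---|
| 40/15 (planned) | 60/60 | 95.0% | 2.6% | 0.0% | 95.0% | 95.2% |
| 40/15 | 55/65 | 93.8% | 3.6% | 0.0% | 95.0% | 95.3% |
| 40/15 | 20/40 | 92.0% | 4.5% | 0.0% | 95.3% | 95.2% |
| 40/15 | 40/20 | 97.3% | 1.3% | 0.0% | 95.2% | 95.4% |
| 90/15 | 60/60 | 93.0% | 5.7% | 0.01% | 94.6% | 96.1% |
| 90/10 | 60/60 | 95.3% | 3.9% | 0.2% | 94.1% | 95.4% |
| 95/5 | 60/60 | 93.5% | 5.8% | 14% | 95.9% | 94.6% |
| 95/3 | 60/60 | 90.3% | 9.3% | 28% | 94.8% | 96.2% |
| 98/2 | 60/60 | 90.8% | 8.9% | 69% | 91.0% | 96.6% |
| 90/15 | 20/20 | 88.4% | 10.8% | 24% | 94.1% | 94.4% |

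A simulation of the full treatment plus eye-side model, with 30 subjects per cell, agrees: 94.8% at 40/15, 93.5% at 95/5 and 90.7% at 98/2.

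**Effect on the decision.** At 60 per arm, no table has the ANOVA lower limit above 0 with a Pearson test that is not significant at 0.05. Four tables go the other way, with Pearson significant in favour of AG-920 but the limit at or below 0. Their total probability at 40/15 is 0.7%.

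**The case against.** The best defence is that the method works where the trial is planned to be. The only rates in the documents are 15% and 40%, and coverage there with equal arms is 95.0%. That stands.

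A reader might infer that an ANOVA interval on binary data under-covers in general, or whenever rates are extreme. The results do not support that. Coverage is 95.3% at 90/10 and 94.7% at 95/15. It is 95.4% at 5/5 and 98.1% at 2/2, where both rates are low.

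A reader might also infer that the interval loosens the success rule. It does not. The SAP rule ignores it. The protocol rule names no method, so applying the ANOVA interval there is itself a reading of the two documents together. Even on that reading, the limit is slightly stricter than the Pearson test.

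Limits above 100% are remote if placebo stays near 15% with 60 per arm: 0.01% of trials at 90/15 and 0.1% at 95/15. Only 9 of the 3,721 tables produce one, all with an observed difference of at least 95 points.

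Finally, Newcombe is not a clean replacement. Its upper limit falls below the truth in 5.3% of trials at 90/10 and 9.0% at 98/2, against a nominal 2.5%. This stands, and it is why the fix names a different interval.

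The defence does not cover unequal arms. The shortfall there occurs at the planned rates, and planned subgroups need not be balanced.

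**Conclusion.** The point holds as a minor one about the reported effect size and the subgroup intervals. It does not bear on type I error, on power or on the superiority claim.

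At the planned rates with 60 per arm, coverage is nominal. The loss is about 1 point with 55 active and 65 placebo, and 3 points in a 20/40 subgroup; the reverse imbalance over-covers. At widely separated rates the loss depends on the exact pair: none at 90/10, 2 points at 90/15, about 5 points at 95/3. In a subgroup of 20 per arm at 90/15 it is 6.6 points (95.0 − 88.4).

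These figures assume no eye-side effect. Rates other than 40% and 15%, and arm sizes other than 60, are assumptions.

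**What to change.** In SAP 2.9.1, replace the ANOVA interval with a Miettinen-Nurminen score interval for the risk difference, stratified by study eye side as in the CMH test. Use it for the subgroups in SAP 4.5.1 as well. State that it is the interval meant by the lower-limit condition in Protocol 9.4.6, and reconcile whether that condition belongs to the superiority rule, since the SAP omits it.

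In the tabulated cases this interval covers 94.4% to 96.6%, with better balanced tails than Newcombe at most of the extreme rates, and it cannot pass 100%. In a single stratum its statistic at zero difference is the Pearson statistic multiplied by (N − 1)/N, which is the CMH statistic, so it fits the SAP test. It does not remove the four tables of disagreement with the uncorrected Pearson test.

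The cost is one SAP sentence and a standard software option, to be settled before unmasking. The primary test and the sample size do not change, and the interval is practically the same at the planned rates with equal arms.
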